2. RATIONALE, OBJECTIVES, AND BENEFIT - RISK ASSESSMENT

2.1 RATIONALE FOR PERFORMING THE TRIAL

BI 655130 is in development for the treatment of GPP, PPP, CD, and UC. BI 655130 is currently in Phase II development.

In Phase I studies BI 655130 was mainly administered as intravenous infusion. However, the subcutaneous injection route is considered to be required to enable in upcoming therapeutic studies the self-administration of BI 655130 by patients. For this reason a subcutaneous injection formulation is undergoing clinical development.

Recently, the clinical part of a Phase 1 study (Study 1368-0003) has been completed exploring the characteristics of a subcutaneous formulation of BI 655130 with particular focus on relative bioavailability compared to an intravenous formulation. A further objective was the assessment of local tolerability. In this study, the relative bioavailability of a single SC injection containing of BI 655130 was in a range of about 50% while relative bioavailability increased to 70% for a single SC injection of of BI 655130

To further elucidate the origin of the observed potentially dose dependent increasing bioavailability, the current study will compare the pharmacokinetics (PK) of a single SC injection of of BI 655130 with the PK of two SC injections of of BI 655130. This design will investigate the impact of local factors at the SC injection site on the overall exposure of BI 655130 which may contribute to the lower bioavailability observed in the preceding clinical study.

The current study will also investigate the impact on relative bioavailability regarding the site of injection (abdomen and thigh) to enable the switch of injection site if needed.

To widen the SC dose range the current study will also investigate a subcutaneous dose of of BI 655130 corresponding to two single perumbilical SC injections of (i.e. total injection volume

2.2 TRIAL OBJECTIVES

The primary objective of this trial is to investigate the relative bioavailability of BI 655130 administered as two subcutaneous injections of in the left and right perumbilical region compared to a single subcutaneous perumbilical injection of BI 655130

The secondary objective is to investigate the relative bioavailability of a single subcutaneous injection of BI 655130 into the thigh compared to a single subcutaneous perumbilical injection of BI 655130.

A further objective is to investigate safety, tolerability, and pharmacokinetics of BI 655130 administered as two subcutaneous injections of in the left and right perumbilical region.

Proprietary confidential information © 2019 Boehringer Ingelheim International GmbH or one or more of its affiliated companies

A description of the endpoints to be determined, and the observations along with specific information as how to collect the data for that information, is provided in [Section 5](#).

2.3 BENEFIT - RISK ASSESSMENT

Participation in this study is without any (therapeutic) benefit for healthy subjects. Their participation in the study, however, is of major importance to optimize treatment regimen of the subcutaneous formulation for potential use as maintenance therapy in patients. The subjects are exposed to the risks of the study procedures and the risks related to the exposure to the trial medication.

Procedure-related risks

The use of an indwelling venous catheter for the purpose of blood sampling may be accompanied by mild bruising and also, in rare cases, by transient inflammation of the wall of the vein. In addition, in rare cases a nerve might be injured while inserting the venous catheter, potentially resulting in paresthesia, reduced sensibility, and/or pain for an indefinite period. The same risks apply to veinipuncture for blood sampling.

The total volume of blood withdrawn during the entire study per subject will not exceed the volume of a normal blood donation. No health-related risk to healthy subjects is expected from this blood withdrawal.

Drug-related risks and safety measures

The toxicology package conducted in mice with a mouse-specific antibody (BI 674304) includes 4, 13 and 26-week toxicity studies and reproductive/developmental toxicity studies without any findings which would preclude clinical studies in humans (see IB [\[c03320877-04\]](#)).

The clinical safety and tolerability profile of BI 655130 was comparable to placebo in male subjects following once weekly intravenous doses of up to body weight administered over 4 weeks. There were no deaths or other serious adverse events. There were no dose or exposure related abnormalities in safety laboratory parameters and no safety or tolerability concerns that would preclude further clinical development of BI 655130.

Recently the clinical part of an initial with a subcutaneous formulation has been completed. The maximum tested SC dose was of BI 655130 (injection volume). The study did not reveal systemic or local AEs which would preclude further clinical studies with the SC formulation. The observed exposure at following SC injection was about 6 fold lower compared to the maximum exposure in completed clinical studies with an IV infusion of up to of BI 655130. Therefore even the planned maximum SC dose of of BI 655130 is not expected to exceed exposure limits already tested in humans.

Based on studies in healthy subjects, no specific drug-related risks are anticipated. Nevertheless, the following safety measures are/will be applied in this study in order to minimize the risk for the healthy subjects:

Proprietary confidential information © 2019 Boehringer Ingelheim International GmbH or one or more of its affiliated companies

- The study will start with Dose Group 1 and 2 (perumbilical SC dose of of BI 655130). Provided no dose limiting AEs occurred as approved by the Principal Investigator (or an authorised deputy) and the trial clinical monitor (or an authorised deputy) after in-depth analysis of all available safety data up to Day 10 (see [Section 3.1](#)), the study will pursue with Dose Group 3 (perumbilical SC dose of of BI 655130) and Dose Group 4 (SC dose of of BI 655130 in the thigh). Dose Group 3 will be divided into 2 cohorts. In the first week, 6 subjects will be treated. There will be an interval of at least 1 week after start of dosing in the first cohort before start of dosing of the second cohort of Dose Group 3.
- At any time during the ongoing study, further dosing will be stopped in case of safety and tolerability concerns based on the criteria defined in [Section 3.1](#).
- Monitoring of ECG, vital signs, and extensive safety laboratory testing ([Table 5.2.3:1](#)) is conducted throughout the study.
- After dosing, the subjects will stay at the site for at least 48 hours.
- BI 655130 will be administered in a hospital setting and subjects will be under close medical observation during their hospitalisation (see [Section 6.2](#)), as well as after their discharge and until the end of observation period. Safety will be closely monitored during site visits for both expected and unexpected adverse events.

Currently there are no data available to suggest interactions of BI 655130 [[c03320877-04](#)].

Although rare, a potential for drug-induced liver injury (DILI) is under constant surveillance by sponsors and regulators. Therefore, this study requires timely detection, evaluation, and follow-up of laboratory alterations in selected liver laboratory parameters to ensure subjects' safety, see also [Section 5.2.2.1](#), adverse events of special interest.

Based on the preclinical and clinical information for BI 655130, healthy subjects are not expected to be exposed to undue risks and adverse events in relation to the information expected from this trial. Considering the medical need for the development of an effective and well tolerated drug for the therapy of IBD and GPP, the benefit of this trial is considered to outweigh the potential risks and justifies the exposure of healthy subjects.

3. DESCRIPTION OF DESIGN AND TRIAL POPULATION

3.1 OVERALL TRIAL DESIGN AND PLAN

This study will explore the relative bioavailability, safety, and tolerability following a subcutaneous (SC) injection of BI 655130 at different dose strengths, injection volumes, and injection sites:

- One SC injection of periumbilical (Dose Group 1)
- Two SC injections of each periumbilical left and right (Dose Group 2)
- Two SC injections of each periumbilical left and right (Dose Group 3)
- One SC injection of in the thigh (Dose Group 4)

The total dose in Dose Group 1, 2, and 4 is of BI 655130 and the total dose in Dose Group 3 is of BI 655130.

The study will be conducted in a single-dose, open-label, matched-group design. The exposure in Dose Group 1 will be used as reference to assess the relative bioavailability of Dose groups 2 - 4. For details refer to [Section 4.1](#).

The study will start with Dose Group 1 and 2. After completion of treatment of the first two dose groups, the study will continue with Dose Group 3 and 4. At any time during the ongoing study, further dosing will be stopped in case of safety and tolerability concerns based on the pre-specified trial-specific stopping criteria ([Section 3.3.4.2](#)).

The Dose Group 3 will follow a staggered administration with treatment of 6 subjects (cohort A) in the first week and the remaining subjects (cohort B) from Week 2.

A documented Safety Review of Dose Group 1 and 2 at least 10 days after last dosing in Dose Group 2 must take place prior to continue the study with Dose Groups 3 and 4. An unscheduled safety review meeting can be requested anytime for any reasonable cause by the Principal Investigator (or an authorised deputy) or the sponsor of the study, e.g. because of any unforeseen adverse events. Continuation of the study will only be permitted if no safety concerns exist in the opinion of the Principal Investigator (or an authorised deputy) and the trial clinical monitor (or an authorised deputy). In addition, at least 8 evaluable subjects in each of the Dose Group 1 and 2 are required to decide about continuation with the remaining dose groups.

The minimum data set for review consists of the following data:

- AEs (including clinically relevant findings from ancillary safety testing listed below)
(Note: AEs may be ongoing at the time of Safety Reviews and AE information may be subject to change prior to Database Lock)
- Vital signs
- Clinical laboratory tests
- Check of criteria for stopping subject treatment as per [Section 3.3.4.1](#)

The decision to escalate the dose will be made jointly by the Principal Investigator (or an authorised deputy) and the trial clinical monitor (or an authorised deputy) after in-depth analysis of all available safety data, especially SAEs (if occurred), AEs and out-of-range laboratory results (if considered clinically significant). Safety Reviews can be conducted face-to-face or by video/telephone conference. The trial clinical monitor or a delegate is responsible for organisation and minutes of the reviews. Minutes will be signed off by the Principal Investigator (or an authorised deputy) and filed in the ISF and TMF.

An overview of all relevant trial activities is provided in the [Flow Chart](#). For visit schedule and details of trial procedures at selected visits, refer to [Sections 6.1](#) and [6.2](#), respectively.

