Methodology:	Single dose, open-label in matched-group design			
No. of subjects:				
total entered:	48			
each treatment:	12			
Diagnosis:	Healthy subjects assigned to Dose Group 2 (left and right perumbilical SC injection, of BI 655130), Dose group 3 (left and right perumbilical SC injection, of BI 655130) and Dose Group 4 (SC injection in the thigh, of BI 655130) will be matched for gender and body weight ($\pm 10\%$) to subjects assigned to Dose Group 1 (perumbilical SC injection, of BI 655130).			

Proprietary confidential information © 2019 Boehringer Ingelheim International GmbH or one or more of its affiliated companies

Name of company:		Tabulated Trial Protocol			
Boehringer Ingelheim					
Name of finished product:					
Not applicable					
Name of active ingredient:					
BI 655130					
Protocol date: 25 June 2018	Trial number: 1368-0029		Revision date: 07 January 2019		
Main criteria for inclusion:	Healthy male and female subjects, age of 18 to 50 years, body mass index (BMI) of 19.0 to 29.9 kg/m ²				
Test treatment: dose:	BI 655130	solution for injection			
mode of admin.:	Subcutaneous (SC) injection: 
- Two single injections of perumbilical left and right (Dose Group 2)- Two single injections of perumbilical left and right (Dose Group 3)- One single injection of into the thigh (Dose Group 4)				
Reference treatment: dose:	BI 655130	solution for injection			
mode of admin.:	One single subcutaneous (SC) injection of perumbilical (Dose Group 1)				
Duration of treatment:	One day (single dose) for each treatment				
Criteria for pharmacokinetics:	Primary endpoints: AUC _{0-tz} and C _{max} Secondary endpoints: AUC _{0-∞} Further parameters of interest as appropriate.				
Criteria for safety:	Adverse events (AEs) including clinically relevant findings from the physical examination, local tolerability, safety laboratory tests, 12-lead electrocardiogram (ECG), vital signs (blood pressure [BP], pulse rate [PR]).				

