Statistical methods:	Relative bioavailability will be estimated by the ratios of the geometric means (test/reference) for the primary and secondary endpoints. Additionally, their two-sided 90% confidence intervals (CIs) will be provided. This method corresponds to the two one-sided t-tests procedure, each at the 5% significance level. Since the main focus is on estimation and not testing, an acceptance range was not specified. The statistical model will be an ANOVA on the logarithmic scale including effects for 'treatment', and 'matched pair'. CIs will be calculated based on the residual error from ANOVA. Descriptive statistics will be calculated for all endpoints.				

Proprietary confidential information © 2019 Boehringer Ingelheim International GmbH or one or more of its affiliated companies

FLOW CHART

Visit	Day	Time relative to first drug administration (planned time [h:min])	Approx. time (actual time) [h:min]	Event and comment	PK _{plasma} ⁴	Laboratory/ Urinalysis ³	12-lead ECG	Vital signs (BP, PR)	Query on adverse events, concomitant therapies ⁹	Query regarding local tolerability ⁵
1	-28 to -3			Screening ¹		X ¹²	X	X		
	-5			Ambulatory visit		X ¹¹				
2	-1	-12:00	20:00	Admission to trial site		X ⁸			X	
1	1	-2:00	6:00		X ²					
		0:00	8:00	Drug administration		X ^{2, 12}	X ²	X ²	X ²	X
		0:30	8:30						X	X
		1:00	9:00					X		
		2:00	10:00	Light breakfast ⁶	X			X		
		3:00	11:00		X					
		4:00	12:00	Lunch ⁶	X			X	X	X
		6:00	14:00			X				
		8:00	16:00	Snack (voluntary) ⁶	X			X		
		10:00	18:00	Dinner ⁶						
		12:00	20:00		X			X	X	X
	2	24:00	8:00	Breakfast ⁶	X		X	X	X	X
		28:00	12:00	Lunch ⁶						
		32:00	16:00	Snack (voluntary) ⁶			X			
		34:00	18:00	Dinner ⁶				X	X	
3	48:00	8:00		Breakfast ⁶ discharge from trial site (confirmation of fitness) ⁷	X		X	X	X	X
4	72:00	8:00		Ambulatory visit	X				X	X
5	96:00	8:00		Ambulatory visit	X				X	X
6	120:00	8:00		Ambulatory visit	X				X	X
7	144:00	8:00		Ambulatory visit	X				X	X
8	168:00	8:00		Ambulatory visit	X		X	X	X	X
15	336:00	8:00		Ambulatory visit	X		X		X	X

Proprietary confidential information © 2019 Boehringer Ingelheim International GmbH or one or more of its affiliated companies

Visit	Day	Time relative to first drug administration (planned time [h:min])	Approx. time (actual time) [h:min]	Event and comment	PK _{blood} ⁴	Laboratory/Urinalysis ³	12-lead ECG	vital signs (BP, PR)	Query on adverse events, concomitant therapies ⁹	Query regarding local tolerability ⁵
2	22	504:00	8:00	Ambulatory visit	X	X	X	X	X	X

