7. STATISTICAL METHODS AND DETERMINATION OF SAMPLE SIZE

7.1 STATISTICAL DESIGN – MODEL

7.1.1 Objectives

The trial objectives are stated in [Section 2.2](#).

For the purpose of defining reference and test treatments, the following terminology will be used. The reference treatment (R) will refer to dose group 1, test treatment 1 (T1) refers to dose group 2, test treatment 2 (T2) refers to dose group 4 and test treatment 3 (T3) refers to dose group 3.

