7.2 NULL AND ALTERNATIVE HYPOTHESES

The relative bioavailability of the different dose groups will be estimated by the ratios of the geometric means (test/reference) for the primary and secondary PK endpoints. Additionally, their two-sided 90% confidence intervals (CIs) will be provided. This method corresponds to the two one-sided t-tests procedure, each at the 5% significance level. Since the main focus is on estimation and not testing, an acceptance range was not specified, that is, no hypothesis will be tested.

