## 7.4 PRIMARY ENDPOINT

Analysis of relative bioavailability of the primary endpoints will be performed as defined in Sections 7.1.3 and 7.3.1 of the CTP.

The statistical model for the primary analysis defined in the CTP Section 7.1.3 is an analysis of variance (ANOVA) model on the logarithmic scale. For each matched pair a pair number will be assigned and included in the model as random effect.

The following comparisons will be analysed: T1/R, T2/R and T3/R.

**CTP Section 7.3.1:** *Further comparisons may be investigated if appropriate (e.g. T1 vs. T2 [...] ).*

A sensitivity analysis will be performed with matched pair as fixed effect.

Primary PK endpoints will also be assessed descriptively. The analysis of standard PK parameters is performed according to BI standards ([5](#)) [001-MCS-36-472\_RD-01].

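### T3/R is labelled relative bioavailability, but Dose Group 3 has a higher total dose and nothing corrects for dose, so as written it is an exposure ratio

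*Protocol*

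**What the plan says.** Four places apply the term relative bioavailability to a set of comparisons that includes Dose Group 3.

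- Protocol 3.1: "The exposure in Dose Group 1 will be used as reference to assess the relative bioavailability of Dose groups 2 - 4".
- Protocol 7.2: "The relative bioavailability of the different dose groups will be estimated by the ratios of the geometric means (test/reference"). Section 7.1.1 fixes the coding: "test treatment 3 (T3) refers to dose group 3".
- Synopsis: the test treatments include "Two single injections of perumbilical left and right (Dose Group 3"), and under Statistical methods, "Relative bioavailability will be estimated by the ratios of the geometric means (test/reference) for the primary and secondary endpoints".
- SAP 7.4 opens with "Analysis of relative bioavailability of the primary endpoints will be performed as defined in Sections 7.1.3 and 7.3.1 of the CTP" and continues "The following comparisons will be analysed: T1/R, T2/R and T3/R".

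Protocol 3.1 gives Dose Groups 1, 2 and 4 one common total dose and Dose Group 3 its own: "and the total dose in Dose Group 3 is of BI 655130" (the amount is blacked out). The direction is still legible. Section 4.1.3 adds a highest dose to widen the range, section 3.1 calls the step to the later groups a dose escalation, and the appendix lists 4 vials for Dose Group 3 (10.1.3) against 2 for Dose Group 1 (10.1.1).

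The endpoints in 5.5.1.1 and 5.5.1.2 are AUC0-tz, Cmax and AUC0-∞. The model in 7.1.3 has treatment and matched pair only, and 7.3.1 states no transformation other than the natural logarithm. Section 2.2 asks about relative bioavailability only for two injections against one and for thigh against abdomen. Its third objective, which the rationale in 2.1 points to as Dose Group 3, is safety, tolerability and pharmacokinetics.

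**The concern.** For T1/R and T2/R the total doses are equal, so a ratio of 100% means unchanged bioavailability. For T3/R the same label sits on a ratio that rises with dose alone. A reader who takes the report at its word would see a T3/R well above 100% beside two contrasts where 100% is the neutral value.

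The misreading is not far-fetched here. Section 2.1 motivates the trial by an apparent dose-dependent increase in bioavailability in trial 1368.3. An uncorrected T3/R labelled relative bioavailability would look like confirmation of that signal even if bioavailability had not changed.

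**Working it through.** **1. Reproduce Table 7.6:1.** Inputs from protocol 7.6: 12 per group, two-sided 90% CI, gCV 25, 30 and 35%, precision attained with 95% probability. With 22 degrees of freedom:

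- σ = √ln(1 + gCV²) = 0.2462, 0.2936, 0.3399
- ω = t(0.95, 22) × σ × √(2/12) × √(χ²(0.95, 22)/22)
- precision = exp(ω) = 1.2390, 1.2912, 1.3444

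These are the table's 1.24, 1.29 and 1.34, and all nine rows of limits match to two decimals. The precision figures are not in dispute.

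**2. What T3/R estimates.** Let k = dose(T3)/dose(R). Dose is constant within a group, so dividing each response by its dose changes only the T3 contrast:

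ln(T3/R, dose-normalised) = ln(T3/R, raw) − ln(k)

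Both confidence limits move by the same constant and the standard error does not change. The shift is ln(2) = 0.693 at k = 2 and ln(1.5) = 0.405 at k = 1.5.

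**3. Size.** The doses are blacked out. k = 2 is compatible with 4 against 2 vials but not fixed by it; k = 1.5 is illustrative. Suppose bioavailability is unchanged and pharmacokinetics are linear. The raw T3/R is then 100k%, with limits 100k/precision and 100k × precision.

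| gCV | k = 2: 200% | k = 1.5: 150% | after division by k: 100% |
|---|---|---|---|
| 25% | 161.4 to 247.8 | 121.1 to 185.9 | 80.71 to 123.90 |
| 30% | 154.9 to 258.2 | 116.2 to 193.7 | 77.45 to 129.12 |
| 35% | 148.8 to 268.9 | 111.6 to 201.7 | 74.38 to 134.44 |

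For example, at gCV 30% and k = 2: 200/1.2912 = 154.9 and 200 × 1.2912 = 258.2. The last column is the set of Table 7.6:1 rows for a ratio of 100%.

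**4. How the protocol uses the term elsewhere.** Table 1.2.5:3 gives geometric mean AUC0-∞ in trial 1368.3 of 574 and 1600 for the two SC groups and 2280 for IV. Section 1.2.5 reports bioavailability of about 50% and 70%.

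- 1600/2280 = 70.2%, which agrees with 70% without any correction.
- 574/2280 = 25.2%, which needs a factor of 50/25.2 = 1.99 to reach 50%.
- Between the two SC groups the raw ratio is 1600/574 = 2.79, against 70/50 = 1.4 on the bioavailability scale.

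The 50% figure must therefore be dose-corrected. The protocol uses one term in two senses.

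**The case against.** The strongest reply is that section 2.2 already limits relative bioavailability to Dose Groups 2 and 4, and section 7.1.1 refers back to it. On that view only loose wording remains. This is true of the objectives, but it confirms the inconsistency: 3.1 names Dose Groups 2 to 4 outright, and 7.2 refers to all the dose groups. The synopsis and SAP 7.4 are less explicit, since there the label on T3/R comes from a general statement read together with a list. Sections 7.1.2 and 7.3.1 and SAP 7.5.2 do not themselves label T3/R and need no correction.

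Second, redacted text might contain dose-normalised parameters. The list in 5.5.1.3, parts of the SAP and the PK SOP cannot be seen, so this is possible. However, 7.1.2 ties relative bioavailability to the primary and secondary endpoints, and 7.3.2 keeps the further parameters descriptive. A hidden parameter of that kind would not change the modelled T3/R.

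Third, a dose covariate would be aliased with treatment, and the raw T3/R is a valid contrast. Both statements are right. The model is not at fault; what is missing is a known offset or a different label.

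Fourth, reading T3/R as k times relative bioavailability assumes clearance independent of dose and, for Cmax, unchanged absorption kinetics, while 1.2.5 suggests target-mediated disposition. This stands as a limit on interpretation, including of the dose-normalised ratio. The ln(k) difference between raw and normalised ratios does not depend on it.

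Finally, the sponsor evidently dose-corrected in trial 1368.3 and may well do so again. That makes the harm less likely, but the plan should say so.

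**Conclusion.** The concern holds, as a minor point. Followed literally, the plan reports T3/R as relative bioavailability without correcting for Dose Group 3's higher total dose. The direction is established by legible text; the size depends on the blacked-out dose ratio. The error is a constant ln(k) on the log scale, so with unchanged bioavailability and linear pharmacokinetics the reported figure would be about 200% at k = 2 or 150% at k = 1.5, where the corrected figure is 100%.

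The effect is confined to one contrast that serves neither the primary nor the secondary objective in an estimation-only trial. T1/R, T2/R, the precision of 1.24, 1.29 and 1.34, and the 48 subjects are unaffected. The raw T3/R is sound as an exposure ratio; its label is wrong.

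**What to change.** Either of two changes is enough.

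- **(a) Dose-normalise.** Where T3/R is reported as relative bioavailability, fit the same model to dose-normalised AUC0-tz, Cmax and AUC0-∞ or, equivalently, subtract ln(dose ratio) from the log estimate and both limits. Label the uncorrected T3/R an exposure ratio. State that the normalised ratio also reflects any departure from dose proportionality and the different number of injections.
- **(b) Relabel.** Limit the relative-bioavailability wording in the synopsis, protocol 3.1 and 7.2 and SAP 7.4 to Dose Groups 2 and 4, in line with 2.2, and report T3/R as an exposure ratio.

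Option (a) costs a sentence in each document and one constant per endpoint. Option (b) is a wording change in four places. Neither needs new data, more subjects or a new sample-size calculation.
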